Xxxxx/ yyyy/ zz/ v/ uuuuuu	Visit x	Xxxx/ yyyyy/ ddmmmyyyy	Хххх (уууу)	Xx/ yyy	Not Returned	N/A	N/A	XXXXX
			Хххх (уууу)	Xx/ yyy	Returned/ ddmmmyyyy	Good/ xxx	xxx	-

IP: Investigational Product, BFS: Blow Fill Seals

\$: Stage 2 = Moderate, Stage 3 = Severe

Note: - = unknown or not evaluated, N/A = not applicable, NA = North America, EU = Europe

Analysis dataset: ADxx.SAS7BDAT;
Date/time of run: ddmmmyyyy:hh:mm

program name>

Programming Note:

See section 15 for Format of output in the SAP. Sort listing by treatment group (lowest MT8 to highest and then Vehicle) and patient ID and visit.

Sponsor: Recordati Rare Diseases; Protocol No.: REC0559-B-001

Listing 16.2.5.2.1 MT6 plasma concentrations (PK)

Patient ID/ Treatment group/ Region/ Disease stage \$/ Study eye	Study Drug Administration Date and Time (Study Day)	Visit	Scheduled Time	Sample Collected?	Collection Date and Time (Study Day)	Deviation in Sample Collection Time (min) (Actual Time - Planned Time)	Concentration (ng/mL)
Xxxxx/ REC 0/0559 0.5 µg/day/ NA/ 2/ Right	Ddmmmyyyy hh:mm (xx)	Visit 1b	Pre-dose	Yes	Ddmmmyyyy hh:mm	N/A	BLQ
, - , -			10 min post-dose	Yes	Ddmmmyyyy hh:mm (xx)	3	Xxx
			20 min post-dose	No	-	-	-
	Ddmmmyyyy hh:mm (xx)	Visit 3	Pre-dose	Yes	Ddmmmyyyy hh:mm (xx)	N/A	BLQ
			10 min post-dose	Yes	Ddmmmyyyy hh:mm (xx)	4	Xxx
			20 min post-dose	Yes	Ddmmmyyyy hh:mm (xx)	2	XXX
Xxxxx/ yyyy/ zz/ v/ uuuuuu	Ddmmmyyyy hh:mm	Visit 1b	Pre-dose	Yes	Ddmmmyyyy hh:mm	N/A	BLQ
			10 min post-dose	Yes	Ddmmmyyyy hh:mm (xx)	3	Xxx
			20 min post-dose	Yes	Ddmmmyyyy hh:mm (xx)-	0	xxx

BLQ: Below limit of quantification

\$: Stage 2 = Moderate, Stage 3 = Severe

Note: - = unknown or not evaluated, N/A = not applicable, NA = North America, EU = Europe

Note: Study Day 1 is the first day of study treatment.

Analysis dataset: ADxx.SAS7BDAT;
Date/time of run: ddmmmyyyy:hh:mm

program name>

Programming Note:

See section 15 for Format of output in the SAP. Sort listing by treatment group (lowest REC 0/0559 to highest and then Vehicle) and patient ID and by visit and time point.

This document is confidential.

SAP Version: 1.0, 31-May-2024

Controlled Document ID: 3903A.02, Effective Date 31-Aug-2020

Sponsor: Recordati Rare Diseases; Protocol No.: REC0559-B-001

Listing 16.2.5.2.2 MT6 plasma PK parameters (PK)

Patient ID/ Treatment group/ Region/ Disease stage \$/ Study eye	Study Drug Administration Date and Time (Study Day)	Timepoint	AUC ₀₋₄ (h*ng/mL)/ AUC _T (h*ng/mL)	C _{max} (ng/mL)/ C _{max ss} (ng/mL)	AUC _{0-t} (h*ng/mL)	T _{max} / T _{max} ss	Ctrough
Xxxxx/ REC 0/0559 0.5 µg/day/ NA/ 2/ Right	Ddmmmyyyy hh:mm (xx)	х	xx	xxx	xxx	xxx	xxx
IIII, Z, Rigite	Ddmmmyyyy hh:mm (xx)	Х	xxx	XXX	XXX	XXX	XXX
Xxxxx/ yyyy/ zz/ v/ uuuuuu	Ddmmmyyyy hh:mm (xx)	х	xx	xx	xx	xx	xx

AUC_T: Area under the plasma concentration-time curve during the dosage interval (4 hrs) for the first administration, C_{max} : Maximum plasma concentration, C_{max} : Maximum plasma concentration, C_{max} : Time to peak plasma concentration at steady state, AUC_0-4 (Day 1): Area under the plasma concentration-time curve from zero to 4 hours post the 1st daily administration, AUC_0-t: Area under the concentration-time curve from time zero to the last measurable concentration, C_{trough} : Trough plasma concentration\$: Stage 2 = Moderate, Stage 3 = Severe

Note: - = unknown or not evaluated, N/A = not applicable, NA = North America, EU = Europe

Note: Study Day 1 is the first day of study treatment.

Note: Concentration values below the assay's lower limit of quantification (BLQ) in pre-dose Visit 1b (Day 1) samples are treated as zero and the sampling time of pre-dose samples relative to dosing are also treated as zero. All BLQ values occurring after Visit 1b (Day 1) are set to ½ lower limit of quantification (LLQQ).

Analysis dataset: ADxx.SAS7BDAT;
Date/time of run: ddmmmyyyy:hh:mm

oprogram name>

Programming Note:

See section 15 for Format of output in the SAP. Sort listing by treatment group (lowest REC 0/0559 to highest and then Vehicle) and patient ID and by visit and time point.

This document is confidential.

SAP Version: 1.0. 31-May-2024

Controlled Document ID: 3903A.02, Effective Date 31-Aug-2020

Sponsor: Recordati Rare Diseases; Protocol No.: REC0559-B-001

Listing 16.2.6.1 Grading Form for Corneal Images - Central Reading (Enrolled Set)

Patient ID/ Treatment group/ Region/ Disease stage \$/ Study eye	Visit	Date of Examination (Study Day)	Examination	Result
Xxxxx/ REC 0/0559 0.5 µg/day/ NA/ 2/ Right	Visit x	Ddmmmyyyy (xx)	Complete corneal healing (no fluorescein staining)	No
			Complete corneal healing (<0.5 mm fluorescein staining)	No
			White to white diameter (pixel)	XXXX
			Maximum dimension of lesion (pixel)	xxx
			Maximum dimension of lesion (%) *	XX
			Maximum dimension of lesion (%) (derived) *	XX
			Reduction (%) of greatest diameter from Visit la (derived)	xxx.xx
			> 20% Reduction of greatest diameter from Visit 1a (derived)	Yes
			>= 50% Reduction of greatest diameter from Visit 1a (derived)	Yes
			Area of cornea (pixels)	XXXXXXX
			Area of lesion (pixels)	XXXXXX
			Percentage (%) of corneal surface affected	XX
			Percentage (%) of corneal surface affected (derived)	XX
			Is there staining elsewhere on the cornea?	Yes - Not
				Persistent
			Comment	-
	Visit y	Ddmmmyyyy (xx)	Complete corneal healing (no fluorescein staining)	Yes
			Complete corneal healing (<0.5 mm fluorescein staining)	Yes
Xxxxx/ yyyy/ zz/ v/ uuuuuu	Visit x	Ddmmmyyyy (xx)	Complete corneal healing (no fluorescein staining)	No
			Complete corneal healing (<0.5 mm fluorescein staining)	No
	Visit y	Ddmmmyyyy (xx)	Complete corneal healing (no fluorescein staining)	No

^{*:} Percentage of corneal diameter

Note: - = unknown or not evaluated, N/A = not applicable, NA = North America, EU = Europe

Note: Study Day 1 is the first day of study treatment.

Analysis dataset: ADxx.SAS7BDAT;

This document is confidential.

SAP Version: 1.0, 31-May-2024

Controlled Document ID: 3903A.02, Effective Date 31-Aug-2020

^{\$:} Stage 2 = Moderate, Stage 3 = Severe

Sponsor: Recordati Rare Diseases; Protocol No.: REC0559-B-001

Programming Note:

See section 15 for Format of output in the SAP. Sort listing by treatment group (lowest REC 0/0559 to highest and then Vehicle) and patient ID, visit, start date and examination as ordered on the CRF. If a patient is not treated or a screen failure display 'Not Treated' or 'Screen Failure' in first column as Treatment group and sort these patients at the end of the listing.

This document is confidential.

SAP Version: 1.0, 31-May-2024

Controlled Document ID: 3903A.02, Effective Date 31-Aug-2020

Statistical Analysis Plan – Table and Figure Shells
Sponsor: Recordati Rare Diseases; Protocol No.: REC0559-B-001

Listing 16.2.6.2 Slit Lamp Cornea and Fluorescein Test - Investigator Assessment (Enrolled Set)

Patient ID/ Treatment group/ Region/ Disease stage \$/	Euro	Visit	Date of Assessment	Test	Aggoggmont	Result/Reason Not Done
Xxxxx/ REC 0/0559 0.5 µg/day/	Eye Study	Visit x	(Study Day) Ddmmmyyyy (xx)	Fluorescein	Assessment PED or corneal ulcer present?	Yes
NA/ 2/ Right					Type: Location	PED: Involve the central cornea, Involve inferior-nasal
					Length of the greatest dimension (mm) Length of the greatest perpendicular dimension (mm)	xxx
					Complete corneal healing (no fluorescein staining) Complete corneal healing (<0.5 mm	No Yes
					fluorescein staining) Oxford scale grade	1
					Reduction (%) of greatest diameter from Visit la *	XXX
					> 20% Reduction of greatest diameter from Visit 1a #	No
					>= 50% Reduction of greatest diameter from Visit la #	No
				Slit Lamp	Cornea	Dellen, Infection Stromal swelling
		Visit y 	Ddmmmyyyy (xx)	Fluorescein	PED or corneal ulcer present? Type: Location	Yes PED: Involve the central cornea, Involve inferior- nasal
				Slit Lamp	 Cornea	Infection
	Fellow	Visit x	Ddmmmyyyy (xx)	Fluorescein Slit Lamp	NK present? Cornea	No Dellen
		Visit y	Ddmmmyyyy (xx)	Fluorescein	NK present?/ Stage Oxford scale grade	Yes/ 1 3
Xxxxx/ yyyy/ zz/ v/ uuuuuu	Study	Visit x	Ddmmmyyyy (xx)	Fluorescein	PED or corneal ulcer present?	Yes

This document is confidential.

SAP Version: 1.0, 31-May-2024 Controlled Document ID: **3903A.02**, Effective Date 31-Aug-2020 Filing requirements: TMF

Sponsor: Recordati Rare Diseases; Protocol No.: REC0559-B-001

Patient ID/ Treatment group/ Region/ Disease stage \$/ Study eye	Eve	Visit	Date of Assessment (Study Day)	Test	Assessment	Result/Reason Not Done
_Study eye	пЛе	VISIC	(Study Day)	1630	Type: Location	Corneal Ulcer: Involve the central cornea

PED = Persistent Epithelial Defects, NK = Neurotrophic Keratitis

- *: Reduction is calculated as (greatest diameter [mm] at visit) / (greatest diameter [mm] at Visit 1a) * 100
- #: > 20% and >= 50% reduction (Yes/No) is derived based on assessment 'Reduction (%) of greatest diameter from Visit 1a'
- \$: Stage 2 = Moderate, Stage 3 = Severe

Note: - = unknown or not evaluated, N/A = not applicable, NA = North America, EU = Europe

Note: Study Day 1 is the first day of study treatment.

Note: Examination of the fellow eye is scheduled only at screening (V1a) and end of treatment (V8/EoT).

Analysis dataset: ADxx.SAS7BDAT;
Date/time of run: ddmmmyyyy:hh:mm

program name>

Programming Note:

See section 15 for Format of output in the SAP. Sort listing by treatment group (lowest REC 0/0559 to highest and then Vehicle) and patient ID, eye (display first study eye then fellow eye), visit, start date and test and assessments as ordered on the CRF. Add derived endpoints for Reduction of greatest diameter at the end of Fluorescein Test results for each visit. If a patient is not treated or a screen failure display 'Not Treated' or 'Screen Failure' in first column as Treatment group and sort these patients at the end of the listing. If multiple slit lamp results for the cornea separate by comma in the Results column.

This document is confidential.

SAP Version: 1.0. 31-May-2024

Controlled Document ID: 3903A.02, Effective Date 31-Aug-2020

Sponsor: Recordati Rare Diseases; Protocol No.: REC0559-B-001

Listing 16.2.6.3 Best Corrected Distance Visual Acuity (BCDVA) (Enrolled Set)

Patient ID/ Treatment group/ Region/ Disease stage \$/ Study eye	Eye	Visit	Date of Assessment (Study Day)	Assessment	Result
Xxxxx/ REC 0/0559 0.5 µg/day/ NA/ 2/ Right	Study	Visit x	Ddmmmyyyy (xx)	ETDRS Letter Score (4m)	xxx
-				ETDRS Letter Score (1m)	xx
				Total ETDRS Letter Score (derived)	xxxx
				Difference of Total ETDRS Letter Score to Visit 1a (derived)	XXX
				If zero (0) letters read correctly at 1m indicate best visual acuity	Hand motion
		Visit y	Ddmmmyyyy (xx)	ETDRS Letter Score (4m)	xxx
				Total ETDRS Letter Score (derived)	xxxx
				Difference of Total ETDRS Letter Score to Visit 1a (derived)	xxx
	Fellow	Visit x	Ddmmmyyyy (xx)	ETDRS Letter Score (4m)	xxx
			- 1111		
Xxxxx/ yyyy/ zz/ v/ uuuuuu	Study	Visit x	Ddmmmyyyy (xx)	ETDRS Letter Score (4m)	xxx
, ,				Total ETDRS Letter Score (derived)	XXXX

ETDRS: Early Treatment Diabetic Retinopathy Study

\$: Stage 2 = Moderate, Stage 3 = Severe

Note: - = unknown or not evaluated, N/A = not applicable, NA = North America, EU = Europe

Analysis dataset: ADxx.SAS7BDAT;

Programming Note:

See section 15 for Format of output in the SAP. Sort listing by treatment group (lowest REC 0/0559 to highest and then Vehicle) and patient ID, eye (study eye first, then fellow eye), visit, start date and Assessment as ordered on the CRF. If a patient is not treated or a screen failure display 'Not Treated' or 'Screen Failure' in first column as Treatment group and sort these patients at the end of the listing.

This document is confidential.

SAP Version: 1.0, 31-May-2024

Controlled Document ID: 3903A.02, Effective Date 31-Aug-2020

Sponsor: Recordati Rare Diseases; Protocol No.: REC0559-B-001

Listing 16.2.6.4 Time to Event Endpoints (Enrolled Set)

Patient ID/ Treatment group/ Region/ Disease stage \$/ Study eye	Endpoint	Occurrence of ICE/ Date (Study Day)	Treatment Start Date	Event/Censoring Date (Study Day)	Duration (days)
Xxxxx/ REC 0/0559 0.5 µg/day/ NA/ 2/ Right	Complete corneal healing (no fluorescein staining) - central reading	N/A	Ddmmmyyyy	Ddmmmyyyy	xxx
, , ,	Complete corneal healing (no fluorescein staining) - investigator	N/A	Ddmmmyyyy	Ddmmmyyyy	XXX
	Time to at least 50% corneal healing - central reading	N/A	Ddmmmyyyy	Ddmmmyyyy	XXX
	Time to at least 50% corneal healing - investigator Time to onset (> 20%) of corneal healing - central reading	N/A N/A	Ddmmmyyyy Ddmmmyyyy	Ddmmmyyyy Ddmmmyyyy *	XXX
	Time to onset (> 20%) of corneal healing - investigator	N/A	Ddmmmyyyy	Ddmmmyyyy *	XXX
Xxxxx/ yyyy/ zz/ y/ uuuuuu	Complete corneal healing (no fluorescein staining) - central reading	ICE3/ Ddmmmyyyy (xx)	Ddmmmyyyy	-	xxx §
	Complete corneal healing (no fluorescein staining) - investigator assessment	ICE3/ Ddmmmyyyy (xx)	Ddmmmyyyy	_	xxx §
	Time to at least 50% corneal healing - central reading	ICE3/ Ddmmmyyyy (xx)	Ddmmmyyyy	-	xxx §
	Time to at least 50% corneal healing - investigator assessment	ICE3/ Ddmmmyyyy (xx)	Ddmmmyyyy	-	xxx §
		ICE3/ Ddmmmyyyy (xx)	Ddmmmyyyy	-	xxx §
Xxxxx/ yyyy/ zz/ v/ uuuuuu	Complete corneal healing (no fluorescein staining) - central reading	ICE1/ Ddmmmyyyy (xx)	Ddmmmyyyy	Ddmmmyyy #	xxx
	Complete corneal healing (no fluorescein staining) - investigator assessment	ICE1/ Ddmmmyyyy (xx)	Ddmmmyyyy	Ddmmmyyy #	XXX
Xxxxx/ yyyy/ zz/ v/ uuuuuu	Complete corneal healing (no fluorescein staining) - central reading	N/A	Ddmmmyyyy	Ddmmmyyyy *	XXX

^{*:} Event, #: Censored at available Week 8 assessment date, §: Set to Day 56 as last scheduled efficacy assessment date as planned per protocol if no assessment date at Week 8 is available

This document is confidential.

SAP Version: 1.0, 31-May-2024

Controlled Document ID: 3903A.02, Effective Date 31-Aug-2020

^{\$:} Stage 2 = Moderate, Stage 3 = Severe

Note: - = unknown or not evaluated, N/A = not applicable, NA = North America, EU = Europe, ICE = Intercurrent Event, LOCF = Last Observation Carried Forward, ICE1: Treatment discontinuation due to treatment-related AE, ICE2: Treatment discontinuation due to other reasons, ICE3: Start of rescue treatments/procedures, ICE4: Treatment discontinuation due to death

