5.4. Other Efficacy Endpoints

- Percentage of patients achieving complete corneal healing of PED or corneal ulcer at Week 8, defined as the greatest diameter of corneal fluorescein staining in the area of the PED or corneal ulcer < 0.5 mm as assessed by central reading.
- Percentage of patients achieving complete corneal healing of PED or corneal ulcer at Week 8, defined as the greatest diameter of corneal fluorescein staining in the area of the PED or corneal ulcer < 0.5 mm as assessed by the investigator.

This document is confidential.

Filing requirements: TMF

- Percentage of patients achieving complete corneal clearing at Week 8, defined as a score of 0
 using the Oxford scale.
- Time to at least 50% corneal healing (defined as a ≥ 50% reduction in the greatest diameter of the lesion) as determined by central reading.
- Time to at least 50% corneal healing (defined as a ≥ 50% reduction in the greatest diameter of the lesion) as determined by the investigator.
- Time to onset of healing (defined as a > 20% reduction in the greatest diameter of the lesion) as determined by central reading.
- Time to onset of healing (defined as a > 20% reduction in the greatest diameter of the lesion) as determined by the investigator.

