8.2. Key Definitions

Baseline and change from baseline:

The baseline value will be defined as the last available measurement before the first administration of study treatment.

Change from baseline = (post-baseline value – baseline value).

Percentage change from baseline = (change from baseline / baseline value) * 100

Study day:

The study day is calculated relative to the day of first study drug administration, i.e., the first day of study drug administration is designated as Day 1. The day after is Day 2 and so forth until end of study (EOS). The preceding day to Day 1 is designated as Day -1, the day before Day -1 is Day -2, etc.

Calculation of duration

Applicable for adverse events, medical history, and concomitant medication.

If times are available and if the duration is less than 24 hours, the duration will be calculated as (end date/time – start date/time) and presented in hh:mm. If at least 1 time is missing or if the duration is at least 24 hours, it will be calculated as (end date - start date) + 1 and presented in days.

In case of partial/missing start or end date, duration will not be calculated.

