The time from treatment start to at least 50% corneal healing is defined as a \geq 50% reduction in the greatest diameter of the lesion as determined by a central reader in days. Treatment group and randomisation strata are used as covariates. Patients who do not achieve at least 50% corneal healing until end of treatment (V8/D56) are censored at date of V8/D56 or last available date if early terminated in case no intercurrent event (ICE) occurred. The censoring date after the occurrence of an ICE and respective imputation will be the actual assessment date at (V8/D56), if available. In case the patient has no efficacy assessment done at (V8/D56), the censoring time (days) after the ICE occurrence will be set to Day 56, which is the last scheduled efficacy assessment day in the 8 week treatment administration period as planned per protocol. The analysis will be performed on the mITT population according to the estimand framework and ICE definitions for the time to event endpoints (Section 7.2). Missing data will be imputed with single value imputation as per Section 8.3.2.

The HRs and their 95% Wald CIs and p-values, as well as the estimate and 95% CI for the median, 25% and 75% quartiles of time to at least 50% corneal healing, will be reported in a table; the survival probability for the treatment groups will be plotted in a figure.

10.4.5. Other Efficacy Endpoint 5

The time from treatment start to at least 50% corneal healing was defined as a \geq 50% reduction in the greatest diameter of the lesion as determined by the investigator in days. Treatment group and randomisation strata are used as covariates. Patients who do not achieve at least 50% corneal healing until end of treatment (V8/D56) are censored at date of V8/D56 or last available date if early terminated in case no intercurrent event (ICE) occurred. The censoring date after the occurrence of an ICE and respective imputation will be the actual assessment date at (V8/D56), if available. In case the patient has no efficacy assessment done at (V8/D56), the censoring time (days) after the ICE occurrence will be set to Day 56 which is the last scheduled efficacy assessment day in the 8 week treatment administration period as planned per protocol. The analysis will be performed on the mITT population according to the estimand framework and ICE definitions for the time to event endpoints (Section 7.2). Missing data will be imputed with single value imputation as per Section 8.3.2.

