The time from treatment start to onset of healing was defined as a > 20% reduction in the greatest diameter of the lesion as determined by the investigator in days. Treatment group and randomisation strata are used as covariates. Patients who do not achieve > 20% reduction until end of treatment (V8/D56) are censored at date of V8/D56 or last available date if early terminated in case no intercurrent event (ICE) occurred. The censoring date after the occurrence of an ICE and respective imputation will be the actual assessment date at (V8/D56), if available. In case the patient has no efficacy assessment done at (V8/D56), the censoring time (days) after the ICE occurrence will be set to Day 56 which is the last scheduled efficacy assessment day in the 8 week treatment administration period as planned per protocol. The analysis will be performed on the mITT population according to the estimand framework and ICE definitions for the time to event endpoints (Section 7.2). Missing data will be imputed with single value imputation as per Section 8.3.2.

The HRs and their 95% Wald CIs and p-values, as well as the estimate and 95% CI for the median, 25% and 75% quartiles of time to onset of corneal healing, will be reported in a table; the survival probability for the treatment groups will be plotted in a figure.

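### The footnote to SAP Listing 16.2.6.2 computes percent reduction in lesion diameter as percent remaining, so the >=50% flag is inverted and the >20% flag is wrong at true reductions of 20% or less and 80% or more

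*SAP*

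**What the plan says.** Listing 16.2.6.2 in SAP section 20.2 shows, by patient and visit, the investigator's lesion measurements and three derived rows: a percent reduction in greatest diameter from Visit 1a, and Yes/No flags for a reduction above 20% and of at least 50%.

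- The first footnote gives the formula: "Reduction is calculated as (greatest diameter [mm] at visit) / (greatest diameter [mm] at Visit 1a) * 100".
- The second footnote ties both flags to that value: "reduction (Yes/No) is derived based on assessment 'Reduction (%) of greatest diameter from Visit 1a".
- The programming note treats the rows as endpoint derivations: "Add derived endpoints for Reduction of greatest diameter at the end of Fluorescein Test results for each visit".

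Elsewhere the SAP describes the quantity correctly:

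- SAP 10.4.5 (Other Efficacy Endpoint 5) requires at least a "50% reduction in the greatest diameter of the lesion as determined by the investigator in days".
- SAP 10.4.7 (Other Efficacy Endpoint 7) requires more than a "20% reduction in the greatest diameter of the lesion as determined by the investigator in days".
- SAP 5.4, Protocol 6.2.3 and the shells for Tables 14.2.3.5.1 and 14.2.3.7.1 use equivalent wording.
- SAP 8.2 gives the general rule, in which change is post-baseline minus baseline: "Percentage change from baseline = (change from baseline / baseline value) * 100".

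Listing 16.2.6.1 (central reading) has rows of the same name, such as "50% Reduction of greatest diameter from Visit 1a (derived", but gives no formula.

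**The concern.** A reduction needs a subtraction, and the footnote has none. A lesion that has not changed scores 100% and one that has disappeared scores 0%, the reverse of what the row label says. Both flags depend on that number, so the error passes into them.

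At stake are Other Efficacy Endpoints 5 (time to at least 50% healing) and 7 (time to onset of healing), both by investigator assessment. Fluorescein staining is first repeated at Visit 2 (Day 3 +/-1). If the event dates come from these flags, every patient who still has half or more of the Visit 1a diameter at that visit has an Endpoint 5 event at about Day 3. Every patient with more than 20% of the diameter left has an Endpoint 7 event. A patient already healed by then has neither. The Kaplan-Meier and Cox results would not measure healing.

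If the programs do not follow the footnote, the listing prints a formula that disagrees with its own values.

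**Working it through.** **Inputs.** d0 = greatest diameter at Visit 1a and d = greatest diameter at the visit (Listing 16.2.6.2). Visit 1a is the only pre-dose staining assessment in the schedule, so it is also the baseline under SAP 8.2. Thresholds: >20% (SAP 10.4.7) and >=50% (SAP 10.4.5). The plan states no numerical result to reproduce; the check compares two formulas.

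**Formulas.**

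- Footnote: L = 100 * d / d0.
- True reduction, the negative of the percentage change in SAP 8.2: T = 100 * (d0 - d) / d0.
- Adding the two: L + T = 100, so L = 100 - T.

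**>=50% flag.** The footnote gives Yes when L >= 50, that is, T <= 50. The endpoint needs T >= 50. The two agree only at T = 50.

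**>20% flag.** The footnote gives Yes when L > 20, that is, T < 80. The endpoint needs T > 20. The two agree for 20 < T < 80. The footnote gives a false Yes at T <= 20 and a false No at T >= 80.

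**Example with d0 = 4 mm** (an illustrative value):

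| d (mm) | Footnote L | True T | >20%: footnote / true | >=50%: footnote / true |
|---|---|---|---|---|
| 4.8 | 120% | -20% | Yes / No | Yes / No |
| 4 | 100% | 0% | Yes / No | Yes / No |
| 3.6 | 90% | 10% | Yes / No | Yes / No |
| 3.2 | 80% | 20% | Yes / No | Yes / No |
| 3 | 75% | 25% | Yes / Yes | Yes / No |
| 2 | 50% | 50% | Yes / Yes | Yes / Yes |
| 1.6 | 40% | 60% | Yes / Yes | No / Yes |
| 0.8 | 20% | 80% | No / Yes | No / Yes |
| 0.7 | 17.5% | 82.5% | No / Yes | No / Yes |
| 0 | 0% | 100% | No / Yes | No / Yes |

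**Count over whole-percent values of T from 0 to 100.** The >20% flag is wrong at 0 to 20 (21 values) and 80 to 100 (21 values), so 42 of 101. The >=50% flag is wrong at 101 - 1 = 100 of 101. Any growth (T < 0) gives L > 100 and Yes on both flags. A finer sweep in steps of 0.1 points from -50% to 100% gives the same regions and boundaries.

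These are counts of grid points. They are not expected proportions of patients, because the documents give no distribution of lesion reductions.

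**The case against.** The strongest reply is that this is one footnote in a by-patient listing. The endpoint definitions, the shells that report Endpoints 5 and 7, and the general rule in SAP 8.2 are all right. The time-to-event data have their own listing (16.2.6.4), which does not refer to these flags. SAP section 10 places algorithms in the ADaM metadata and specifications, which are not part of these documents. The phrase in the programming note may only say where the rows are displayed. Reach is also limited: these are other efficacy endpoints, and SAP 10.3 extends the gatekeeping to secondary endpoints only.

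Most of this stands, and it limits the consequence: damage to Endpoints 5 and 7 is a risk, not a demonstrated result. It does not remove the error. The footnote is the only explicit formula for reduction in diameter in either document, it is specific to this variable where SAP 8.2 is generic, and no rule says that body text overrides it. Followed as written, it gives wrong values and flags in the listing itself. The formula also runs without a fault and, for any lesion that has not grown, returns values between 0 and 100, so a visual check could miss it.

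For the central reading no error is shown. The missing formula in Listing 16.2.6.1 is a point for clarification only.

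**Conclusion.** The concern holds. The formula gives percent remaining under a label of percent reduction. It makes the >=50% flag wrong at every true reduction except exactly 50%, and the >20% flag wrong at 20% or less and at 80% or more, including lesions that grow.

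The listing error is certain if the shell is followed. The effect on Endpoints 5 and 7 depends on whether the analysis datasets use the same derivation, which the documents do not show. The No/No result for a healed lesion assumes that its diameter is recorded as 0 mm. Endpoints 4 and 6 (central reading) are not shown to be wrong. The primary, key secondary and secondary endpoints and the sample size are untouched. It should be fixed because the error is definite, the endpoint risk is real and the correction is trivial.

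**What to change.** Replace the first footnote of Listing 16.2.6.2 with: Reduction (%) = (greatest diameter at Visit 1a - greatest diameter at visit) / greatest diameter at Visit 1a * 100. A lesion at 0 mm then scores 100% and Yes/Yes, an unchanged lesion scores 0% and No/No, and both flags match the endpoint definitions at every value. The second footnote can stay as it is.

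Confirm that the ADaM specification for Endpoints 5 and 7 uses this formula.

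For clarity, state the same formula under Listing 16.2.6.1, name the lesion measure that enters it (that listing shows the maximum dimension in pixels and as a percentage of corneal diameter), and extend the specification check to Endpoints 4 and 6.

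The cost is one line of shell text in each of two listings and one specification check. No new data are needed.
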